5.4 Randomization Criteria

Subjects will be randomized into the study provided they have satisfied all subject selection criteria.

5.5 Lifestyle Considerations

Following consent to participate in the study by completing the ICF, subjects may be asked to remove any leave on cosmetics (including make-up) prior to the visit assessments.

During the entire study (Screening – Last Subjects Last Visit (LSLV)) the following must be avoided:

- Making a change to current facial care habits and practices, including the addition or removal of any new facial topical product to their current regimen and/or switching brands of facial topical products, other than as defined in this protocol.
- Introduction of new home care products which may come into contact with the skin, including laundry detergent, shower gel, shampoo, bath soap.
- Intentional exposure to artificial ultraviolet (UV) light or sunbathing.

- Undergoing any non-invasive, minimally-invasive or invasive cosmetic or surgical procedures on the face, e.g. waxing, bleaching etc.

Visit 2:

- Prior to the final visit (Visit 2), subjects must not apply any topical products (including leave-on cosmetics) to their face other than their assigned product.
- Subjects must cleanse their face with either tap water or their current cleanser in the morning prior to site visit and apply their assigned product for the final use, 2-4 hours prior to the visit.
- Subjects must refrain from drinking caffeinated drinks (e.g. coffee, tea, cola etc.) prior to Visit 2.

5.6 Screen Failures

Screen failures are defined as subjects who consent to participate in the clinical study but are not subsequently randomized. To ensure transparent reporting of screen failure subjects, a minimal set of screen failure information will include demography, screen failure details (e.g. withdrawal of consent), eligibility criteria, and any adverse events or incidents as applicable.

Individuals who do not meet the criteria for participation in this study (screen failure) will not be re-screened.

5.7 Sponsor's Qualified Medical Personnel

Contact information for the sponsor's appropriately qualified medical personnel for the study is documented in the Study Contact List located in the investigator study master file held at the study site.

The contact number is only to be used by investigational staff seeking advice on medical questions or problems in the event that the established communication pathways between the investigational site and the study team are not available.

The contact number is not intended for direct use by study subjects. To facilitate access to appropriately qualified medical personnel on study-related medical questions or problems, subjects will be provided with a contact card. The contact card will provide, as a minimum, protocol identifiers, the subject's study identification number, contact information for the investigational site, and contact details in the event that the investigational site cannot be reached to provide advice on a medical question or problem identified by a healthcare professional other than the investigator.

5.8 Clinical Assessor Qualifications

All clinical assessments will be made by a single qualified dermatologist and a single qualified ophthalmologist for all subjects throughout the study. Each assessor will visually assess subjects for eligibility to continue in the trial and at the end of the 21 (+2) day product use period.

The intensity of any visual signs of dermal irritation will be recorded according to the grade of the reactions in the Dermatological Evaluation ([Safety and Other Assessments](#)). The dermatologist is responsible for grading the level of cutaneous irritation and their opinion on the correct classification of the irritation scores is final. The same dermatologist will be used to evaluate all subjects in the study.

The intensity of any visual signs of ocular irritation will be recorded according to the grade of the reactions in the Ophthalmological Evaluation ([Safety and Other Assessments](#)). The

ophthalmologist is responsible for grading the reactions, their opinion on the classification of the ocular irritation scores is final. The same ophthalmologist will be used to evaluate all subjects in the study.

Any observed cutaneous or ocular response that can be denoted according to the grade of the reactions will not be considered an adverse event. Only in the case of unusual reactions, in the opinion of the clinical expert, will these reactions and the consequences observed upon evaluation be documented as AEs.

6 INVESTIGATIONAL/STUDY PRODUCTS

For the purposes of this study, per International Conference on Harmonization (ICH) guidelines, and GSK policy, investigational product is defined as a pharmaceutical form of an active ingredient, a non-medicinal product (marketed or investigational), or a placebo, being tested or used as a reference (positive or negative control), in a clinical trial. This includes a product with a marketing authorization when used or assembled (formulated or packaged) in a way different from the approved form, or when used for an unapproved indication, or when used to gain further information about an approved use.

6.1 Investigational/Study Product Supplies

The following study products will be supplied by the Clinical Supplies Department, GSK CH:

Table 6-1 Investigational/Study Product Supplies

| | Investigational Product | Reference Product |
|---------------------------------------|---|--|
| Product Name | Developmental Serum | Physiogel Calming Relief Anti-Redness Serum (Korean market place product) |
| Product Formulation Code (MFC) | CCI [REDACTED] | CCI [REDACTED] |
| Product Format | 30 ml Bottle with piston pump | |
| Dispensing Details | A kit will be dispensed to each subject containing 2 bottles | |
| Application Quantity | To be used as per normal home use application | |
| Route of Administration | Topical dermal (facial) application | |
| Application Instructions | Apply twice daily to freshly cleansed skin in place of your current serum and before your moisturizer | |
| Return Requirements | All used/unused samples to be returned to the study site | |

The contents of the label will be in accordance with all applicable regulatory requirements and will be the responsibility of the Clinical Supplies Department, GSKCH.

Other items to be supplied by the clinical investigational site:

- Aqueous Lactic Acid solution (10%) – For LAST
- Saline solution (0.9 Molar) – For LAST
- Cotton Buds - For LAST

Supplies provided by the clinical investigational site must also be stored in compliance with the label requirements in a secure place with limited or controlled access.

Detailed instructions for the return of study product/study supplies for the accountability checks and subsequent destruction will be provided by GSKCH during the course of the study in time for study close out visit.

6.1.1 Dosage Form and Packaging

Both the developmental serum and the comparator serum will be supplied to the clinical site as labelled packaged bottles for dispensing by the site staff. The commercial bottles will have the commercial labels removed.

The content of the product labels will be in accordance with all applicable regulatory requirements and will be the responsibility of the GSK CH Global Clinical Supplies group. Each study label will contain, but not be limited to, protocol number, container number, directions for use and storage requirements.

Care should be taken with the supplied products and their labels so that they are maintained in good condition. It is important that all labels remain intact and legible for the duration of the study. Subjects should be instructed to not remove or deface any part of the study label.

All products supplied are for use only in this clinical study and should not be used for any other purpose.

6.1.2 Preparation and Dispensing

Both the investigational product and the reference product will be dispensed by qualified unblinded site personnel according to the randomization schedule. These staff members will not be involved in any safety or other aspects of the study that could be influenced by the knowledge of product a subject has been assigned to. An additional site member of site staff, should ensure the dispensing procedures are completed accurately.

Subjects will be assigned to products in accordance with the randomization schedule generated by an approved GSK CH vendor, prior to the start of the study, using validated software.

6.2 Administration

The first application of product will be under supervision at the study site at Visit 1 (Day1) following baseline subject self-assessment questions, dermatologist and ophthalmologist assessments and the LAST.

Subjects will be instructed to self-administer their assigned product per the usage instructions.

6.2.1 Dosing Errors

Dosing errors may result, in this study, from the administration or consumption of:

- the wrong product,
- by the wrong subject,
- at the wrong time,
- or at the wrong dosage.

Dosing errors occurring to a study subject are to be captured in the Case Report Form (CRF). In the event of a medication dosing error, the sponsor should be notified immediately.

Dosing errors are reportable irrespective of the presence of an associated AE, including:

- Dosing errors involving subject exposure to any of the study products;
- Potential dosing errors or uses outside of what is foreseen in the protocol that do or do not involve the participating subject.

If a dosing error is accompanied by an AE, as determined by the investigator, the dosing error and, any associated adverse event(s) are to be captured in the CRF AE form.

6.3 Investigational/Study Product Storage

The investigator, or designee, will ensure that all products are stored in a secured area with controlled access under required storage conditions and in accordance with applicable regulatory requirements and the product label.

Site systems must be capable of measuring and documenting (for example, via a log), at a minimum, daily minimum and maximum temperatures for all site storage locations (as applicable, including frozen, refrigerated, and/or room-temperature products). This should be captured from the time of first product receipt throughout the study. Even for continuous monitoring systems, a log or site procedure that ensures active daily evaluation for excursions should be available. The operation of the temperature-monitoring device and storage unit (for example, refrigerator), as applicable, should be regularly inspected to ensure it is maintained in working order.

Any excursions from the product-label storage conditions (as detailed on the clinical supplies checklist) should be reported to appropriate site staff upon discovery and communicated to sponsor as soon as possible. The site should actively pursue options for returning the product to the storage conditions as described in the labeling, as soon as possible. Excursions from the storage requirements, including any actions taken, must be documented as a protocol deviation and reported to the Sponsor.

Once an excursion is identified, the affected product (or products) must be quarantined and not used until the sponsor provides documentation of permission to use. Use of any of the affected product(s) prior to sponsor approval will be considered a protocol deviation.

Site staff will instruct subjects on the proper storage requirements for all take-home products.

6.4 Investigational/Study Product Accountability

All products supplied are for use only in this clinical study and should not be used for any other purpose.

All products must be received by a designated person at the study site, handled and stored safely and properly, and kept in a secured location to which only the staff have access. Upon receipt, all study products should be stored according to the instructions specified on the product labels. Study products are to be dispensed only to subjects enrolled in the study in accordance with the protocol, by authorized site staff.

The investigative site must maintain adequate records documenting the receipt, use, loss, or other disposition of all the product supplies. All study products will be accounted for using the investigational/study product accountability form/record. The investigator is responsible for study product accountability, reconciliation, and record maintenance.

The accountability records must be available for inspection by the study monitor during the study. Monitoring of product accountability will be performed by the monitor during site visits and at the completion of the study.

Subjects should return all products to the study site at the end of the study (LSLV) or before if a subject withdrawals/is withdrawn.

6.4.1 Destruction of Investigational/Study Product Supplies

At the conclusion of the study, the Principal Investigator or an appropriate designee, and a representative of GSK CH (study monitor) will inventory all used and unused study products and sundry items. The investigational/study product accountability record for returned study products will then be completed. All study product (used and unused) for this clinical study will be returned for destruction to the GSK CH Clinical Supplies Department or designated vendor using the return instructions provided.

6.5 Blinding and Allocation/Randomization

All subjects will be centrally randomized to one of the two study arms using an Interactive Response Technology (IRT). Before the study is initiated, training, login information and directions for the IRT will be provided to the site. Study products will be dispensed according to the instruction received through the IRT at the appropriate study visit.

Returned study products should not be re-dispensed to any subject.

The investigator's knowledge of the product allocation should not influence the decision to enroll a particular subject or affect the order in which subjects are enrolled.

This study is described as examiner-blind (the clinical examiners (dermatologist, ophthalmologist) will be blinded to the product received). The study statistician, data management staff, other employees of the Sponsor and vendors acting on behalf of the sponsor, who may influence study outcomes will also be blinded to the product allocation.

To ensure the examiners remain blinded throughout the study, staff involved in the preparation and dispensing of study products will work in a separate area. The examiners are not permitted in any area where study product is stored, dispensed, or in use.

Subjects will be instructed not to remove study products from the opaque bags outside of the dispensing room, while at the study site. Dispensing staff will not be involved in any safety assessment procedures during the study.

6.6 Breaking the Blind

At the initiation of the study, the study site will be instructed on the method for breaking the blind. The method will be an electronic process.

The electronic system will be programmed with blind-breaking instructions. In case of an emergency, the investigator has the sole responsibility for determining if unblinding of a subject's product assignment is warranted. Subject safety must always be the first consideration in making such a determination. If the investigator decides that unblinding is warranted, the investigator should make every effort to contact the sponsor prior to unblinding a subject's product assignment unless this could delay emergency treatment of the subject.

If a subject's product assignment is unblinded, the sponsor must be notified within 24 hours after breaking the blind. The date and reason that the blind was broken must be recorded in the source documentation and case report form, as applicable.

Any AE associated with breaking the blind must be recorded and reported as specified in this protocol. The study site may also be required to inform the EC if the blind is broken.

6.7 Subject Compliance

Study products will be administered under the supervision of investigator site personnel for the first application.

A paper diary will be supplied to promote compliance and to capture details of product use throughout the study period. Subjects may also record additional information such as AEs or medications used. Any additional details relevant to efficacy or safety must be reviewed by the investigator (or suitably qualified designee) with the subjects, and transcribed to the CRF as appropriate.

The number of any missed or additional applications will be captured as protocol deviations and transcribed from the diary into the CRF. Subjects will be re-instructed in the correct usage requirements and diary completion as needed.

6.8 Concomitant Medication/Treatment(s)

Any medications, treatments or vaccines (including over-the-counter or prescription medicines, vitamins, and/or herbal supplements) taken during the study, from signing the informed consent, must be recorded in the CRF with indication, reason for use, unit dose, daily dose, and start and stop dates of administration. All subjects will be questioned about concomitant medication/treatments at each site visit.

Medication/treatments taken within 30 days of signing the informed consent form will be documented as a prior medication/treatment. Medications/treatments taken after signing the informed consent form will be documented as concomitant medication/treatments.

Subjects should abstain from all concomitant treatments, except for contraceptives and those used for the treatment of adverse events.

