2 INTRODUCTION

In recent years the cosmetic industry has grown considerably, along with its concern for developing safe and effective products. Heightened industry awareness, consumer and regulatory agency requirements have led cosmetic manufacturers to adopt procedures that provide a robust assessment of the risks and benefits of their products. This includes the conduct of clinical tests to assess safety and efficacy, which are often coordinated by dermatologists or other experts before marketing a new product. These procedures provide greater assurance of safety for cosmetic manufacturers, increasing their credibility and confidence among consumers.

A cosmetic product on the market must not cause damage to human health when applied under normal or reasonably foreseeable conditions of use, taking into account, in particular, the product's presentation, its labelling, and any instructions. (Cosmetics Europe, 2004)

Skin contact with topical products such as cosmetics may trigger different types of reactions including eczema, contact dermatitis, urticaria, acne and spots. Contact dermatitis can arise from two mechanisms: primary irritation, through the action of irritant substances; or sensitization, in the presence of an allergenic ingredient (Birmingham, 1965).

Clinical studies to evaluate the irritation and sensitization potential of a product must consider a number of variables including the components used in the formulation, ingredient concentration, absorption, amount applied, skin condition, application directions and frequency, as well as the cumulative effect (Dooms-Goossens, 1993). The most common form of intolerance to cosmetics is characterized by irritation, burning sensation, redness, pruritus and erythema at the application site (Lumelsky *et al.*, 2001).

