7 DISCONTINUATION OF STUDY INTERVENTION AND SUBJECT DISCONTINUATION/WITHDRAWAL

7.1 Subject Discontinuation/Withdrawal

A subject may withdraw from the study at any time at his or her own request, or may be withdrawn at any time at the discretion of the investigator or sponsor for safety, behavioral reasons, or the inability of the subject to comply with the protocol-required schedule of study visits or procedures.

The following circumstances require discontinuation of study product and/or premature subject withdrawal:

- Protocol violation that may impact the subject's safety
- Withdrawal of informed consent
- Subject lost to follow-up
- Unblinding of the subject
- Pregnancy

If a subject is discontinued or prematurely withdraws from the study, the reason(s) for discontinuation or withdrawal and the associated date must be documented in the relevant section(s) of the CRF.

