8.1.11 Supervised Product Application

Sufficient product will be provided to last the complete study period. Subjects will use the product at home, twice a day during the study period of 21 (+ 2) days, including the morning of the final visit and will be instructed to contact the study site if they have any reactions.

Subjects will be dispensed a paper diary alongside their assigned product to be completed at home to record product use.

Spontaneous reporting of adverse events and those elicited by asking subjects to respond to a non-leading question such as "How do you feel?" will be assessed and any AEs recorded in the CRF.

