4.3.2 Prior and Concomitant Medication

Prior or concomitant medication taken by or administered to a subject will be recorded in the case report form. The prior and concomitant medications will be coded using an internal validated medication dictionary, GSKDrug.

As justified within Section 5, the current analysis standards for defining concomitant medications will be used rather than those provided in the protocol (which defined concomitant based on the timing of providing informed consent):

- Prior medications are defined as those which stopped before the first application of the study product.

- Concomitant medications are defined as the medication ongoing or started on or after the first application of the study product.

Prior and concomitant medication will be listed (PPD [redacted] and PPD [redacted]) by subject, with drug name, GSK drug synonym, dose, dose form, frequency, route, start date/ study day relative to first study product administration, and ongoing or end date/ study day relative to first study product administration.

Unknown dates will not be imputed, however, if the start or stop date is unknown, then it will be assumed to be a concomitant medication (unless a partial start date / stop date indicates otherwise).

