4.4 Analysis of Tolerability

4.4.1 Primary Tolerability Endpoint

4.4.1.1 Primary Tolerability Endpoint Definition

The primary endpoint will be the change from baseline (prior to any product application) in dermatologist signs and symptoms of cutaneous irritation total score following 21 (+2) days of product use.

This study will be considered a success if at least 90% of completed subjects do not have a significant increase (i.e. a unit increase score of 1 in the total score) from baseline in dermatologist assessed signs and symptoms of cutaneous irritation following 21 (+2) days of investigational product use.

Calculation of dermatologist assessment of signs and symptoms of cutaneous irritation total score and change from baseline in total score:

The cutaneous irritation total score will be calculated in the following way:

Cutaneous irritation total score = dermal response score of erythema + dermal response score of dryness + dermal response score of scaling + dermal response score of edema

Where, the dermal response score is described in [Table 4-1](#).

Table 4-1 Dermatological Evaluation

Attribute	Description (Score)				
Erythema	None (0)	Very Slight (0.5)	Slight (1)	Moderate (2)	Severe (3)
Dryness	None (0)	Very Slight (0.5)	Slight (1)	Moderate (2)	Severe (3)
Scaling	None (0)	Very Slight (0.5)	Slight (1)	Moderate (2)	Severe (3)
Edema	None (0)	Very Slight (0.5)	Slight (1)	Moderate (2)	Severe (3)

For example, if the dermal responses score of erythema = 2, dermal responses score of dryness = 0.5, dermal responses score of scaling = 1 and dermal responses score of edema = 0.5.

Then the cutaneous irritation total score will be:

$$\text{Total score} = 2 + 0.5 + 1 + 0.5 = 4.$$

Change from baseline in dermatologist signs and symptoms of cutaneous irritation total score = total score at day 21 – total score at baseline.

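### A product reaction that is treated as an adverse event and has cleared by Day 21 counts as a success under the 90% rule, and the SAP has no rule for it

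*Protocol*

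**What the plan says.** **Treatment allowed.** Protocol 6.8: "Subjects should abstain from all concomitant treatments, except for contraceptives and those used for the treatment of adverse events". There is no limit by class, site or timing. Exclusion 17 bars immunosuppressants, antihistamines, NSAIDs and corticosteroids, but only for the two weeks before screening.

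**What becomes an adverse event.** Under Protocol 5.8 a response that fits the grading scale is not an adverse event. The exception reads "Only in the case of unusual reactions, in the opinion of the clinical expert, will these reactions and the consequences observed upon evaluation", and such reactions are documented as AEs. The Introduction says that contact with cosmetics "may trigger different types of reactions including eczema, contact dermatitis, urticaria, acne and spots".

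**What happens to a reactor.** Under Protocol 8.1.11 subjects "will be instructed to contact the study site if they have any reactions". Protocol 7.1 opens its mandatory list with "The following circumstances require discontinuation of study product and/or premature subject withdrawal". Neither a skin reaction nor its treatment is on that list.

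**The success rule.** SAP 4.4.1.1, repeating Protocol section 3, requires that "at least 90% of completed subjects do not have a significant increase (i.e. a unit increase score of 1 in the total score" after 21 (+2) days of the investigational product. The dermatologist scores at baseline and at Visit 2 only.

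**Records.** Protocol 6.8 says that medications "must be recorded in the CRF with indication, reason for use, unit dose, daily dose, and start and stop dates of administration". The SAP 4.3.2 listing is specified "with drug name, GSK drug synonym, dose, dose form, frequency, route, start date/ study day relative to first study product administration", followed by the end date or ongoing status. Reason for use is not among its fields.

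**The concern.** The event being treated may be caused by the product, and the treatment is meant to clear the signs that the dermatologist scores. A facial urticaria or contact dermatitis in week 2 that is settled with an antihistamine or a steroid leaves a clear face at Day 21. The rule then counts that subject as tolerating the serum.

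Nothing else in the plan corrects the count. SAP 4.4.3 covers only missing data and withdrawals. SAP 4.1.2 treats prohibited medication as a possible important deviation, which is tabulated and listed, whereas treatment of an adverse event is permitted. The heading of SAP 4.3 mentions rescue medication, but no text below it links such use to the endpoint. The blinded review may exclude data (Protocol 12.2.2) or subjects (SAP 4.1.3), and exclusion removes a reactor instead of counting her as a failure.

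The 90% rule is the only stated success criterion and no inference accompanies it. At worst, a product whose reactions needed anti-inflammatory treatment is declared well tolerated.

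**Working it through.** **Inputs.** At least 30 completers per arm and 90 randomized (Protocol 12.1). The 30 rests on clinical considerations and a guideline minimum, so there is no power figure to reproduce. I use n = 30, and n = 45 = 90/2 for no losses under equal allocation, which is my assumption. A failure is taken as a rise of 1 or more in the total score.

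**Step 1: failures allowed.** The rule needs at least 0.9n subjects without a failure.
- n = 30: 27 needed, so at most 3 failures.
- n = 45: 0.9 × 45 = 40.5, so 41 needed and at most 4 failures.

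**Step 2: effect of one treated reactor.** This needs no assumed rate.

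| Completers | Would fail untreated | None treated | One treated and clear | One excluded |
|---|---|---|---|---|
| 30 | 4 | 26/30 = 86.7%, fails | 27/30 = 90.0%, passes | 26/29 = 89.7%, fails |
| 45 | 5 | 40/45 = 88.9%, fails | 41/45 = 91.1%, passes | 40/44 = 90.9%, passes |

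At n = 30 it takes two exclusions to change the result: 26/28 = 92.9%. These cases are chosen at the threshold; away from it one subject changes nothing.

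**Step 3: illustration with assumed rates.** Let p be the share who would fail untreated and s the share of those who are treated and clear at Day 21. Then P(pass) = P(X ≤ k), with X ~ Binomial(n, p(1 − s)) and k = 3 or 4. Neither p nor s is in the documents.

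| p | s | n = 30 | n = 45 |
|---|---|---|---|
| 5% | 0 | 0.939 | 0.927 |
| 5% | 10% | 0.956 | 0.949 |
| 5% | 50% | 0.994 | 0.995 |
| 15% | 0 | 0.322 | 0.175 |
| 15% | 10% | 0.409 | 0.256 |
| 15% | 50% | 0.816 | 0.754 |

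At p = 5% and s = 10% the shift is about 2 points. The 15% rows are illustrative only, because they let any subject with a graded rise be treated, and 6.8 does not permit that.

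**Step 4: cost of a loose correction.** Suppose the new rule failed every subject who treated any facial event, and this added 2% of subjects as false failures. At p = 5% the failure rate becomes 5% + 2% = 7%, and P(pass) falls from 0.939 to 0.845 (n = 30) and from 0.927 to 0.795 (n = 45). That loss exceeds the bias being corrected at p = 5%, so the rule needs a relatedness condition.

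**The case against.** **The permitted route is narrow.** Ordinary graded irritation is not an adverse event, so treating it is outside the 6.8 exception. Protocol 5.5 bars adding facial topicals throughout the study other than as the protocol defines, and allows only the assigned product on the face before Visit 2. The route is therefore mainly systemic treatment of an unusual reaction, or topical AE treatment stopped before Visit 2, in a subject whose graded score would also have been up by 1 at Day 21. This stands and limits the size. It does not close the gap: a subject who treats graded irritation against the rules may be a deviation, but her Day 21 score still counts.

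**The endpoint is a Day 21 state by design.** An untreated reaction that resolves also counts as a success. That is true, and the fix does not try to change it. A reaction that needed an anti-inflammatory drug is nevertheless different evidence about tolerance from one that settled unaided.

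**The blinded review may deal with it.** SAP section 4 leaves its agenda open, and SAP 4.1.2 refers further deviations to a review listing document that is not in hand. However, no documented outcome counts a treated reactor as a failure. Discretionary withdrawal under 7.1 would also take her out of the completed subjects.

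**The reactions would be visible.** SAP 4.6.1 provides treatment-related AE tables by skin category and a skin AE listing. A reader might infer that the plan hides reactions, and it does not. But those tables do not feed the 90% rule and do not contain treated graded irritation.

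**Conclusion.** The gap is real: following the plan exactly can score a product reaction that needed treatment as a tolerance success. The bias favours the product, since treatment is meant to clear the reaction and exclusion removes a reactor. The documents give no rate, and the number of such subjects is probably small. One subject matters only near the threshold, as in Step 2.

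A reader might infer from Step 3 that the chance of passing rises from 32% to between 41% and 82% at n = 30. The documents do not support that. It assumes a 15% failure rate and makes every graded reactor eligible for treatment, whereas 5.8 and 6.8 confine permitted treatment to reactions recorded as adverse events. A reader might also infer that 6.8 expressly allows steroids and antihistamines; it only sets no class limit.

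This is a cheap improvement. The conclusion rests on the text of 6.8, 7.1 and the success rule, not on any assumed rate.

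**What to change.** Settle this before unblinding.

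1. Add one sentence to SAP 4.4.1.1: a completed subject who, after first application, took a corticosteroid, antihistamine, NSAID or immunosuppressant for a facial skin reaction judged product-related counts as not meeting the criterion and stays in the denominator. Product-related means a treatment-related skin AE, or graded facial irritation given as the reason for use and not attributed to another cause at the blinded review. Use for any other reason, such as headache or hay fever, leaves the observed score in place.
2. Beside the pass/fail figure, print the as-observed Day 21 percentage and the number of such subjects per arm.
3. Add reason for use to the SAP 4.3.2 listing.
4. Record the departure from Protocol section 3 in SAP Table 5-1. Protocol 6.8 can stay as it is.

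**Cost.** One sentence, one listing column, a few figures in the primary table and one Table 5-1 entry. Reason for use, dates, causality and the skin category are already planned. The downside is that a subject who treated a related rise of less than 1 unit becomes a failure: with 3 true failures of 30, one such subject turns 27/30 = 90.0% into 26/30 = 86.7%. The as-observed percentage shows when that has happened.
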